5. RESOURCES AVAILABLE TO CONDUCT THE HUMAN RESEARCH

- *Explain the feasibility of meeting recruitment goals of this project and demonstrate a potential for recruiting the required number of suitable subjects within the agreed recruitment period*
 - *How many potential subjects do you have access to?*
- *Describe your process to ensure that all persons assisting with the trial are adequately informed about the protocol and their trial related duties and functions*

COVID-19 cases are still prevalent in New York, and another surge is anticipated from March to May according to Infectious Disease experts. We have seen a significant increase in the number of admissions to the hospitals within our healthcare system during past surges. We project we would have access to at least 300 potential subjects.

All persons assisting with the trial will have access to the protocol, and meetings will be arranged to clarify trial related duties and functions via Microsoft Teams.

6. RECRUITMENT METHODS

- *Describe the source of potential subjects*
- *Describe the methods that will be used to identify potential subjects*
- *Describe any materials that will be used to recruit subjects. A copy of any advertisements (flyers, radio scripts, etc.) should be submitted along with the protocol.*
- *If monetary compensation is to be offered, this should be indicated in the protocol*

Recruitment of potential subjects will occur at 7 of the hospitals within the Northwell Health System including Long Island Jewish Medical Center, North Shore University Hospital, Plainview Hospital, Long Island Jewish Valley Stream Hospital, Lenox Hill Hospital, South Shore Hospital and Mather Hospital. Enrollment will first be done at North Shore University Hospital and Long Island Jewish Medical Center with phased-approach expansion to the other sites.

Patients that are admitted with COVID-19 infection within these institutions will be screened for eligibility. The principal investigator and co-investigators will be responsible in obtaining informed consent from those patients who meet eligibility criteria in order to participate in the study. A full discussion of the rationale of the study will be held with the patients and/or their surrogate decision makers to answer any study-related questions. The use of a printed/electronic version of the informed consent will be available for review. All research coordinators will be trained by the principal investigator on non-coercive recruitment approaches. Patients will be clearly informed that their medical care will be of the highest standards regardless of their decision to participate on the study.

No monetary compensation will be offered.

7. ELIGIBILITY CRITERIA

- *Describe the characteristics of the subject population, including their anticipated number, age, ranges, sex, ethnic background, and health status. Identify the criteria for inclusion or exclusion of any subpopulation.*
- *Explain the rationale for the involvement of special classes of subjects, such as fetuses, pregnant women, children, prisoners or other institutionalized individuals, or others who are likely to be vulnerable. You cannot include these populations in your research, unless you indicate such in the protocol*
- *Similarly, detail exclusionary criteria: age limits, special populations (minors, pregnant women, decisionally impaired), use of concomitant medications, subjects with other diseases, severity of illness, etc.*

Over 10,000 patients have been treated in the Northwell Health system with COVID-19 infection. The anticipated demographics of participants in this study will reflect that of severe COVID-19 which has been described to include 60% males and 70% non-white race/ethnicity – the majority of which are African American or Hispanic. Common comorbidities include hypertension, diabetes mellitus, obesity and/or preexisting lung disease.

Inclusion criteria:

- Adults ≥ 18 years
- COVID-19 infection confirmed by a positive PCR test
- Hypoxemia defined by an O₂ saturation $<94\%$ or the need for supplemental oxygen

Exclusion criteria:

- Corticosteroid use for > 48 h within the past 15 days prior to enrollment
- Use of steroids with doses higher than the equivalent to dexamethasone 6 mg
- Use of immunosuppressive drugs
- Pregnant women

Dexamethasone is a fluorinated corticosteroid and has the potential to cause oral clefts or decreased birth weight. When corticosteroids are required in pregnancy, non-fluorinated corticosteroids (e.g. prednisone) is preferred. As we are specifically studying dexamethasone, we are excluding pregnant women to prevent potential harm.

- Chronic oxygen use
- Known history of dexamethasone allergy
- DNR / DNI
- Patient or proxy cannot consent

This study will not preclude participation in other ongoing COVID-19 trials.]

8. NUMBER OF SUBJECTS

- *Indicate the total number of subjects to be accrued locally. If applicable, distinguish between the number of subjects who are expected to be pre-screened, enrolled (consent obtained), randomized and complete the research procedures.*
- *If your study includes different cohorts, include the total number of subjects in each cohort.*
- *If this is multisite study, include total number of subjects across all sites.*

We project screening 300 potential subjects and enrolling 142 patients - 71 in each arm of the study. Accounting for a potential 10% drop out, it will allow us to include at least 128 subjects to achieve statistical power.]

9. STUDY TIMELINES

- *Describe the duration of an individual's participation in the study*
- *Describe the duration anticipated to enroll all study subjects*
- *The estimated date of study completion*

The duration of an individual's participation in the study will be 28 days or until hospital discharge, whichever occurs first.

The duration anticipated to enroll all study subjects is 6 months.

The estimated date of study completion is 12 months.

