4. OBJECTIVE(S)/SPECIFIC AIMS AND HYPOTHESES

- *A concise statement of the goal(s) of the current study.*
- *The rationale for and specific objectives of the study.*
- *The goals and the hypothesis to be tested should be stated.*

The aim of the study is to compare the efficacy of dexamethasone at the current recommended dose versus a higher, weight-based dose. We hypothesize that the use of a higher, weight-based dose of dexamethasone equivalent to 1 mg/kg/day of methylprednisolone would be associated with a decrease in mortality in COVID-19 patients requiring oxygen supplementation.

Primary outcome:

- All-cause mortality at 28 days

Secondary outcomes:

- ICU admission
- ICU length of stay
- Hospital length of stay
- Need for higher oxygen supplementation including venturi mask, non-rebreather mask, high flow nasal cannula or non-invasive mechanical ventilation
- Invasive mechanical ventilation
- Duration of invasive mechanical ventilation
- ECMO
- Need for tracheostomy
- Development of secondary bacterial or fungal infections
- Development of clinically significant hyperglycemia, which will be defined as need for insulin drip or ICU admission to control hyperglycemia
- Oxygen supplementation upon discharge from the hospital
- Subjective symptoms at 28 days
- Disposition upon discharge (home, home with physical therapy, skilled nursing facility, long-term acute care facility, long-term care facility / nursing home, acute rehabilitation facility, hospice care, death)

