10. ENDPOINTS

- *Describe the primary and secondary study endpoints*
- *Describe any primary or secondary safety endpoints*

Primary study endpoint: all-cause mortality at 28 days.

Secondary study endpoints: need for ICU admission, ICU length of stay, hospital length of stay, higher requirements of oxygen supplementation (venturi mask, non-rebreather mask, high-flow nasal cannula or non-invasive mechanical ventilation), invasive mechanical ventilation, duration of invasive mechanical ventilation, ECMO, tracheostomy, subjective symptoms at 28 days, disposition upon discharge, and oxygen supplementation upon discharge.

The primary and secondary safety endpoints will include the development of secondary bacterial or fungal infections that is objectively identified based on culture data, and clinically significant hyperglycemia requiring ICU stay or insulin drip.

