12. STATISTICAL ANALYSIS

- *Describe how your data will be used to test the hypotheses.*
- *State clearly what variables will be tested and what statistical tests will be used.*
- *Include sample size calculations.*

- *If this is a pilot study, state which variables will be examined for hypothesis generation in later studies.*

In general, baseline patient characteristics including demographics and clinical data will be summarized using descriptive statistics for all data combined and data by treatment arm. Specifically, continuous variables will be summarized using mean, standard deviation and median; categorical variables will be summarized using frequencies and percentage. No inferential comparison of treatment arms will be made with respect to baseline and demographic clinical data; such comparisons will be descriptive only. Unless otherwise specified, all results will be considered significant if $p < 0.05$. All data analysis will be performed using SAS 9.4 (SAS institute Inc., Cary, NC). The intent-to-treat (ITT) principle will be employed, i.e all randomized patients in the groups to which they are randomly assigned will be included in the final analysis, regardless of the intervention they actually receive, and regardless of withdrawal from treatment or deviation from the protocol for any reason.

The primary endpoint is all-cause mortality at 28 days. It will be compared between the two treatment arms using chi-squared test or Fisher's exact test.

Among the secondary study endpoints, binary variables (need for ICU admission, need for higher oxygen supplementation including non-rebreather mask, high flow nasal cannula or non-invasive mechanical ventilation, need for invasive mechanical ventilation and need for oxygen supplementation upon discharge) will be compared using chi-squared test or Fisher's exact test between the two arms; continuous variables (ICU length of stay, hospital length of stay, duration of mechanical ventilation) will be compared between the two arms using Kaplan-Meier curve and log-ran test to take into account data censoring.

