Sample size consideration: The sample size calculation was based on the hypothesis of primary endpoint. Our primary hypothesis is that the use of a higher dose of dexamethasone equivalent to 1 mg/kg/day of methylprednisolone would be associated with a decrease in mortality in COVID-19 patients requiring oxygen supplementation. A two group χ^2 test with a 5% two-sided significance level will have 80% power to detect the difference between the proportion of dexamethasone 6 mg group 23.3% and the proportion of dexamethasone weight based 5.9% (odds ratio of 0.206) when the sample size in each group is 64.

To account for 10% dropout rate, will be increasing recruitment to 142, with 71 in each arm to ensure 128 evaluable subjects.

Missing data: If there is less than 5% of an endpoint missing, complete case analysis will be used; if there is more than 5% missing, sensitivity analysis will be performed by assuming all the missing values of an endpoint to be either outcome if it is binary, or by assuming all the missing values of an endpoint to be either upper quartile or lower quartile of the available values if it is continuous, to see if the results are similar to those using complete case analysis.

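### The plan does not provide for collecting oxygen status and disposition at discharge from patients still in hospital on day 28, so two secondary endpoints lose a group selected by outcome

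*Combined protocol and SAP*

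**What the plan says.** - **Follow-up.** Section 9 (Study Timelines): "participation in the study will be 28 days or until hospital discharge, whichever occurs first". The same section expects 6 months of enrolment and completion at 12 months.
- **Endpoints.** Section 10 (Endpoints) ends its list of secondary endpoints with "disposition upon discharge, and oxygen supplementation upon discharge". Section 11 (Research Procedures) lists both among the data to be collected and gives no cut-off day. Section 4 defines the second as "Disposition upon discharge (home, home with physical therapy, skilled nursing facility" and further destinations, ending with "acute rehabilitation facility, hospice care, death". There are eight categories, and none is for a patient who has not left hospital.
- **Analysis.** In Section 12, the binary list closes with "need for oxygen supplementation upon discharge) will be compared using chi-squared test or Fisher's exact test between the two arms". No denominator is stated, and no test is named for disposition. ICU stay, hospital stay and ventilation time get Kaplan-Meier and log-rank methods "to take into account data censoring".
- **Missing data.** Section 12: "If there is less than 5% of an endpoint missing, complete case analysis will be used". Above 5%, a sensitivity analysis sets all missing values to either outcome (binary) or to an upper or lower quartile (continuous).
- **Later follow-up elsewhere.** Section 20 (Privacy) provides a survey or phone call for patients discharged before day 28. Section 16 (Withdrawal) provides for following the record to study end, with permission, for patients who withdraw. Neither covers an inpatient at day 28.

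**The concern.** A patient still in hospital on day 28 has no discharge status when participation ends. The plan foresees incomplete follow-up for the duration endpoints but makes no matching provision for the two endpoints that depend on discharge having happened.

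These values are not missing by accident. The patients concerned are survivors too ill to leave by day 28, so whether the value is missing depends on the course of the illness that treatment is meant to change. If the arms differ in the number of such patients, and such patients leave on oxygen more often than others, a complete-case comparison favours the arm that loses more of them. Leaving them out also sits badly with the statement in Section 12 that all randomised patients enter the final analysis.

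At stake are the oxygen comparison and the completeness of the disposition table. Mortality at 28 days does not depend on discharge and is untouched.

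**Working it through.** **1. The plan's own figure.** The documents give no figure for either discharge endpoint. The only calculation is for the primary endpoint: 23.3% v 5.9%, two-sided 5%, 80% power. With mean proportion 0.146 and difference 0.174:

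n = [1.96·√(2·0.146·0.854) + 0.842·√(0.233·0.767 + 0.059·0.941)]² / 0.174² = 63.5, so 64 per group.

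This agrees with Section 12. The present point does not depend on it.

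**2. When the plan requires a check.** 5% of 142 is 7.1, so up to 7 patients can be dropped with no sensitivity analysis. This takes all 142 as the base and counts only day-28 inpatients as missing. The plan states neither. With 120 survivors as the base, 7 is 5.8% and the check is triggered. If in-hospital deaths also counted as missing for oxygen, the planning rates alone (about 17 + 4 = 21 of 142, 14.8%) would trigger it.

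**3. Bias in the complete-case comparison.** All inputs here are assumed:
- s = 60 day-28 survivors in each arm
- x = 21 of them (35%) truly on oxygen at discharge in each arm, so the true difference is 0
- L = number still in hospital at day 28
- r = proportion of those L who eventually leave on oxygen

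Complete-case proportion = (x − r·L) / (s − L).

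| L, arm A v arm B | r | Arm A | Arm B | False gap (B − A) |
|---|---|---|---|---|
| 1 v 6 (7/142 = 4.9%) | 100% | 20/59 = 33.9% | 15/54 = 27.8% | −6.1 points |
| 3 v 10 (13/142 = 9.2%) | 35% | 35.0% | 35.0% | 0 |
| 3 v 10 | 60% | 19.2/57 = 33.7% | 15/50 = 30.0% | −3.7 points |
| 3 v 10 | 80% | 18.6/57 = 32.6% | 13/50 = 26.0% | −6.6 points |
| 3 v 10 | 100% | 18/57 = 31.6% | 11/50 = 22.0% | −9.6 points |

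The gap needs both conditions: unequal L, and r above the rate in other survivors. Swapping the arms reverses its sign.

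**4. What the plan's check would show.** With r = 100%, the all-on-oxygen run returns 21/60 v 21/60, a difference of 0. For 3 v 10 the all-off-oxygen run gives 18/60 v 11/60 (30.0% v 18.3%, −11.7 points). The two runs together would reveal how fragile the −9.6 is. For 1 v 6, on the base of 142, neither run is required.

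**5. Disposition.** The rule has a binary form and a continuous form. An eight-category variable fits neither, and no category holds the patient still in hospital.

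**The case against.** The strongest reply is that Section 9 states how long a patient participates, not when chart extraction stops. Section 11 takes all data from the electronic record, lists both discharge items with no day-28 limit, and adds no research-only tests. Section 9 is not applied literally elsewhere either, since Section 20 follows discharged patients to day 28. The staff may well intend to read the later chart. This stands to the extent that the text does not make the values unobservable. A reader might infer that they can never be observed, and the documents do not support that. What remains is that no section says they will be collected.

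A second reply is that the plan already has a safeguard. Take the planned deaths (17 v 4 of 71) and assume 4 v 10 still in hospital, with 15/50 v 11/57 of those discharged on oxygen. Complete case gives 30.0% v 19.3% (−10.7 points). Counting the inpatients as on oxygen gives 19/54 v 21/67, 35.2% v 31.3% (−3.8 points). It is tempting to conclude that about two thirds of the apparent benefit is an artefact and that the higher-dose arm will be flattered. But 14/142 is 9.9%, so the plan's own sensitivity analysis would report the second result. Every count except the deaths is also assumed. If the higher dose shortens stays, the bias runs the other way. For oxygen this reply stands above 5% missing, with the limit that complete case remains the reference result.

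Third, disposition has no named test, so no planned comparison can be shown to be biased. That also stands. The gap there is one of definition.

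**Conclusion.** The point holds as a gap in the data-collection plan for two secondary endpoints. As written, patients in hospital at day 28 have no provided-for discharge status, and the missing-data rule removes them. For oxygen, no check is required below 5% missing. Above 5%, a check exists but only as a sensitivity analysis. For disposition, the rule does not apply and no category exists.

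The size is unknown. The documents do not say how many patients will be in hospital at day 28, how they will divide between arms, or how often they leave on oxygen. The figures of about 6 points (1 v 6, all on oxygen) and 0 to about 10 points (3 v 10) show what is possible under the stated assumptions and predict nothing. A reader might go further and infer a bias in favour of the higher dose, or a biased disposition test. The documents support neither: the direction depends on unstated counts, and no disposition test is planned. The primary endpoint is not affected. Severity: minor.

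**What to change.** Amend Section 9, and the data list in Section 11, so that for patients in hospital at day 28 oxygen status and disposition are extracted from the electronic record until actual discharge or death, within the 12-month study period. With 6 months of enrolment, the last patient reaches day 28 about five months before completion. This keeps both endpoints as defined. Redefining them as status at day 28 would instead mix inpatient oxygen use with oxygen need on leaving.

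For anyone still in hospital at data cut-off:
- list them as a separate disposition category;
- for oxygen, report the all-on-oxygen sensitivity result whatever the percentage missing, which also removes the question of which base the 5% refers to.

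Settle this before any outcomes by arm are seen, since Section 11 schedules a look at results after the first 20 patients. The cost is a short amendment, a check that the consent and authorisation wording covers record review after day 28, and a few more weeks of chart review for a few patients.

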10. ENDPOINTS

- *Describe the primary and secondary study endpoints*
- *Describe any primary or secondary safety endpoints*

Primary study endpoint: all-cause mortality at 28 days.

Secondary study endpoints: need for ICU admission, ICU length of stay, hospital length of stay, higher requirements of oxygen supplementation (venturi mask, non-rebreather mask, high-flow nasal cannula or non-invasive mechanical ventilation), invasive mechanical ventilation, duration of invasive mechanical ventilation, ECMO, tracheostomy, subjective symptoms at 28 days, disposition upon discharge, and oxygen supplementation upon discharge.

The primary and secondary safety endpoints will include the development of secondary bacterial or fungal infections that is objectively identified based on culture data, and clinically significant hyperglycemia requiring ICU stay or insulin drip.

11. RESEARCH PROCEDURES

- *Include a detailed description of all procedures to be performed on the research subject and the schedule for each procedure.*
- *Include any screening procedures for eligibility and/or baseline diagnostic tests*
- *Include procedures being performed to monitor subjects for safety or minimize risks*
- *Include information about drug washout periods*
- *If drugs or biologics are being administered provide information on dosing and route of administration*
- *Clearly indicate which procedures are only being conducted for research purposes.*
- *If any specimens will be used for this research, explain whether they are being collected specifically for research purposes.*
- *Describe any source records that will be used to collect data about subjects*
- *Indicate the data to be collected, including long term follow-up*

All hospitalized patients with COVID-19 infection documented by a positive PCR test who require oxygen supplementation or have documented hypoxemia based on oxygen saturation <94% will be screened for eligibility. Baseline diagnostics tests will be as per standard of care and no additional testing is required for our research purposes. All patients will receive routine medical care as per most updated COVID-19 guidelines prior to randomization.

Eligible patients who agree to participate in the study will be randomized 1:1 into two groups. Randomization was set up in REDCap. Once the patient gives consent, the randomization form on REDCap will randomize to either of the groups. As the study is multi-site, the randomization will be stratified by each site.

The standard dexamethasone group will receive a dose of 6 mg daily. The higher dexamethasone group will receive a dose of 0.2 mg/kg/day with maximum dose of 20 mg per day. The route of administration will be IV for both groups. No patients will receive less than dexamethasone 6 mg. The duration of treatment in both arms will be a total of 10 days of steroids or until discharge, whichever comes first.

No procedures, blood draws, imaging or diagnostic testing will be performed on the participants other than those indicated for their medical care.

Data will be obtained from the medical electronic records and tabulated in REDCap. Patient will be de-identified and REDCap access will be limited to appropriate investigators involved in the trial to avoid HIPAA violations.

Data to be collected will include baseline demographic variables, need for higher requirements of oxygen supplementation (venturi mask, non-rebreather mask, high flow nasal cannula or non-invasive mechanical ventilation), ICU admission, invasive mechanical ventilation, duration of invasive mechanical ventilation, tracheostomy, ECMO, length of ICU stay, length of hospital stay, development of secondary bacterial or fungal infections, subjective symptoms at 28 days, development of clinically significant hyperglycemia, oxygen supplementation upon discharge and disposition upon discharge (home, home with physical therapy, skilled nursing facility, long-term acute care facility, long-term care facility / nursing home, acute rehabilitation facility, hospice care, death)

An interim safety and result analysis will be performed after the first 20 patients are enrolled in the study. Subsequent monitoring will occur when 50 and 100 patients are recruited. A designated committee from the study will be assigned for this purpose.]

